An assessment of clinical response will occur at each follow-up visit. The assessment will include parental documentation of maximum temperature in the preceding 24 hours; normalization of respiratory rate; presence and extent of cough; occurrence of medically attended visits including visits to the ED, primary care physician, and urgent care; hospitalizations; use of non-study systemic antibiotics (parenteral or oral); and occurrence of surgical procedures. Vital signs (temperature, pulse and respiratory rates) will be collected at the enrollment visit and at each follow-up visit.

Solicited event assessments will include an assessment of solicited events occurring from the time of enrollment through the last visit, Visit 3. All subjects will complete a subject memory aid from the time of enrollment through Visit 3. Subject memory aids will be reviewed with the subject's parents for any discrepancies or missing data and will be returned to the subject's parent(s).

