9.2 Methods and Timing for Assessing, Recording, and Analyzing Safety Parameters

9.2.1 Adverse Events

Adverse Event (AE): International Conference on Harmonisation (ICH) E6 defines an AE as any untoward medical occurrence in a patient or clinical investigation subject administered a pharmaceutical product regardless of its causal relationship to the study treatment. FDA defines an AE as any untoward medical occurrence associated with the use of a drug in humans, whether or not considered drug related. An AE can therefore be any unfavorable and unintended sign (including an abnormal laboratory finding), symptom, or disease temporally associated with the use of a medicinal (investigational) product.

As the safety profile of amoxicillin, amoxicillin-clavulanate, and cefdinir are well established, and this trial is not powered to detect new, unknown safety signals, **there will be no unsolicited AE collection during this study and only protocol-defined SAE's will be collected.**

Solicited adverse events that are common and known to occur following administration of the study product. Solicited adverse events will be recorded daily for the duration of the study (See Table 3) . In addition to the solicited adverse events specified in Table 3, the presence and severity of cough (Table 2) will be recorded daily for the duration of the study to allow for assessment of the resolution of pneumonia symptoms.

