- Oral, rectal, axillary, or tympanic temperature $\geq 38.3^{\circ}\text{C}$ (100.9°F), confirmed by repeat measurement after at least 15 minutes, in the 24 hours preceding the Outcome Assessment Visit, unless attributed to a new process that is unrelated to the prior diagnosis of pneumonia;

- Elevated respiratory rate (RR >50 breaths/minute for children <24 months of age and >40 breaths/minute for children 24-71 months of age) at the time of the Outcome Assessment Visit;

- Presence of cough grade 2 or 3 at the Outcome Assessment Visit, defined as Grade 0 (no cough), Grade 1 (Occasional coughing [less than 4 times hourly]), Grade 2 (frequent coughing [4 or more times an hour], interferes with sleep), Grade 3 (almost constant coughing (never free of cough), makes sleep nearly impossible);

³ Solicited events will be captured daily until Outcome Assessment Visit #2; thereafter, parents/legal guardians will report symptoms based on memory aid and medical interview by study staff. For those with multiple solicited events, the ordinal response table will be based upon the most severe solicited event.

Day 1: Day 1 begins at the time the first dose of study product is administered and ends at 11:59 PM of that same day. If a subject has no recorded receipt of study product at the time of the analysis, then Day 1 will be defined as the date 5 days after the date of initiation of the initial antibiotic.

DOOR at Outcome Assessment Visit #1: Defined as above, using DOOR components from the following Study Days.

Adequate Clinical Response: Day 1 – Day 5

Resolution of Symptoms:

- o Fever as measured in the 24 hours prior to Outcome Assessment Visit #1. If a subject has a fever according to a single measurement, but no repeat measurement after at least 15 minutes has been performed, the subject will be analyzed as having a fever. If a subject has a fever according to the measurement taken as a part of vital signs

during Outcome Assessment Visit #1, the subject will be analyzed as having a fever at Outcome Assessment Visit #1. If the vital signs measurement shows no fever, and the parental assessment of fever during the previous 24 hours is missing, then fever will be treated as missing.

- o Respiratory Rate and Cough: determined at Outcome Assessment Visit #1

Solicited Events: Day 1 – Day 5

Number of Days of Antibiotic Use: Day 1 – Day 5

DOOR at Outcome Assessment Visit #2: Defined as above, using DOOR components from the following Study Days.

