5. SAMPLE SIZE CONSIDERATIONS

The null hypothesis corresponding to the primary analysis of this study is:

H0: The sum of the probability that a subject assigned to the 5-day arm will have a higher DOOR than if assigned to the 10-day arm plus one-half the probability of equal DOORs is 50% (i.e., no difference in DOOR).

The primary study sample size is based on a superiority test of the null hypothesis above, under an assumed alternative hypothesis that the sum of the probability that a subject assigned to the 5-day arm will have a higher DOOR than if assigned to the 10-day arm plus one-half the probability of equal DOORs is 60% (p=60%).

A sample size of 360 (180 per arm) provides 90% power using a 2-sided alpha=0.05 with a Wilcoxon Mann-Whitney U test (see calculation below). If p=65% or 70%, then a total sample size of 160 (80 per arm) or 90 (45 per arm), respectively, would be required. The sample size is inflated by ~10% based on an estimate from a similar study, in order to account for loss to follow-up resulting in a total sample size of 400 (200/arm).

Sample size calculations were based on the formula below (Noether 1987):

$$N = \frac{(z_{\alpha} + z_{\beta})^2}{12c(1-c)\left(p'' - \frac{1}{2}\right)^2}$$

$$z_{\alpha} = \Phi^{-1}(0.975); z_{\beta} = \Phi^{-1}(0.90); (90\% \text{ power for two-sided test with } 5\% \text{ Type I error})$$

$$c = 0.5 \text{ (equal allocation to treatment arms)}$$

$$p'' = 0.6 \text{ (Pr(Higher DOOR) under alternative hypothesis)}$$

Note that the primary analysis statistical methods use the ITT analysis population and will account for missing data with multiple imputation. The exact analysis method was not used for the power calculation because it would require an excessive amount of assumptions about the nature and patterns of missing data in the final dataset and relationships of components of the imputation model to the primary outcome. Instead, a complete case analysis assuming 90% evaluable for analysis was used to obtain approximately 90% power in the actual analysis.

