8.2.7. Additional Analysis of Cough

The proportion of subjects in each treatment group experiencing moderate or severe cough will be tabulated by day from Day 1 to Day 25 (as recorded from the memory aid), by visit, and overall, with 95% exact confidence intervals ([Table 42](#)). The proportion of subjects in each treatment group experiencing cough will also be tabulated by day from Day 1 to Day 25 (as recorded from the memory aid), by visit, and by severity level ([Table 43](#) and [Table 44](#)). Finally, cough will be analyzed by taking the most severe response over the follow-up period, dichotomizing into a binary variable (none or mild versus moderate or severe) ([Table 45](#)). Proportions for these derived binary variables will be reported along with 95% exact confidence intervals. Comparisons of proportions by treatment groups will be given as odds ratios (with

95% exact confidence intervals) and p-values from Fisher's Exact Tests. Cough severity will be listed by study day and study visit ([Listing 15](#) and [Listing 16](#)).

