8.4. Imputation of Missing Data

8.4.1. Multiple Imputation of Missing Ordinal Clinical Response and DOOR at Outcome Assessment Visit #1 and Outcome Assessment Visit #2

Several analyses, including the primary analysis, depend on multiple imputation of DOOR or OCR at Outcome Assessment Visit #1 or Outcome Assessment Visit #2. Multiple imputations of each of these missing endpoints will be performed independently, and each subject will have their missing endpoints imputed independently of other subject’s imputations using a subject-specific imputation model.

As a first step to multiple imputation, an ordered list of variables to include in the subject-specific imputation model is constructed. Ordering is specified so that exact imputation results from final data are prespecified may be replicated in SAS (using seeds described below). The complete ordered list of variables for the imputation models for DOOR at Outcome Assessment Visit #1 and OCR at Outcome Assessment Visit #1 is below.

- Indicator of subject enrolled at the site with the second most number of subjects enrolled (binary indicator)
- Indicator of subject enrolled at the site with the third most number of subjects enrolled (binary indicator)

-
- Indicator of subject enrolled at the site with the least number of subjects enrolled (binary indicator)
 - Note: the site with the most number of subjects enrolled is reference for site. Language is written to allow for an arbitrary number of sites. In the event of a number of ties for the number of subjects enrolled, tied sites will be ordered in ascending alphanumeric order in the list of model variables.
 - Indicator of amoxicillin (not amoxicillin placebo) as study treatment (binary indicator)
 - Indicator of amoxicillin-clavulanate (not amoxicillin-clavulanate placebo) as study treatment (binary indicator)
 - Indicator of cefdinir (not cefdinir placebo) as study treatment (binary indicator)
 - Note: placebo is the reference group for study treatment
 - Indicator for amoxicillin-clavulanate as initial antibiotic (binary indicator)
 - Indicator for cefdinir as initial antibiotic (binary indicator)
 - Note: amoxicillin is the reference group for initial antibiotic
 - Indicator for age ≥ 2 years at enrollment (binary indicator)
 - Indicator for initial treatment site for pneumonia at an emergency department (binary indicator)
 - OCR at Outcome Assessment Visit #2 (imputed OCRs will not be used)

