 - Severity of cough on Day 1 as recorded on Solicited Events form (0, 1, 2, or 3)
 - Note: amoxicillin is the reference group for initial antibiotic
 - Severity of most severe solicited event (besides cough) on Day 1 (0, 1, 2, or 3)
 - Note: Some missing values for Day 1 will first be imputed as described in Section [6.5.4](#)
 - Severity of cough on Day 2 as recorded on Solicited Events form (0, 1, 2, or 3)
 - Severity of most severe solicited event (besides cough) on Day 2 (0, 1, 2, or 3)
 - Note: Some missing values for Day 2 will first be imputed as described in Section [6.5.4](#)
 - Severity of cough on Day 3 as recorded on Solicited Events form (0, 1, 2, or 3)
 - Severity of most severe solicited event (besides cough) on Day 3 (0, 1, 2, or 3)
 - Note: Some missing values for Day 3 will be first imputed as described in Section [6.5.4](#)
 - Severity of cough on Day 4 as recorded on Solicited Events form (0, 1, 2, or 3)
 - Severity of most severe solicited event (besides cough) on Day 4 (0, 1, 2, or 3)
 - Note: Some missing values for Day 4 will first be imputed as described in Section [6.5.4](#)
-

- Severity of cough on Day 5 as recorded on Solicited Events form (0, 1, 2, or 3)
- Severity of most severe solicited event (besides cough) on Day 5 (0, 1, 2, or 3)
 - Note: Some missing values for Day 5 will first be imputed as described in Section 6.5.4

For DOOR and OCR at Outcome Assessment Visit #2, the complete list of model variables is identical to the above, but with OCR at Outcome Assessment Visit #2 replaced with OCR at Outcome Assessment Visit #1. Additionally, cough severity and most severe solicited event are listed up to Day 18 rather than Day 5.

The actual list of model variables for each subject-specific imputation model will follow the ordering above but omit variables with missing values. The below pseudo-code / SAS code outlines the creation of 20 multiple imputation datasets. Note that the seeds used in the actual analysis must follow the specification given in the pseudo-code and subjects must be processed in the order described in the pseudo-code. OCR will simultaneously be imputed with DOOR at each respective Outcome Assessment Visit. The pseudo-code is in terms of the Outcome Assessment Visit #1 endpoints, but the general logic is also applicable to the Outcome Assessment Visit #2 endpoints (with references to “V1” replaces with references to “V2”).

DEFINE i=index variable for subjects having DOOR imputed.

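### The daily diary predictors used to impute the Visit #1 DOOR stop at Day 5 and include no temperature, although the symptom component is scored on Days 6-10 and the diary covers those days

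*SAP*

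**What the plan says.** SAP 8.4.1 introduces the predictors as "The complete ordered list of variables for the imputation models for DOOR at Outcome Assessment Visit #1" and for the Visit #1 OCR. They are site, study treatment, initial antibiotic, age group, initial treatment setting, the observed OCR at OAV#2, and two daily items: cough grade and worst other solicited event. The daily items run from Day 1 to Day 5 and end with "Severity of cough on Day 5 as recorded on Solicited Events form (0, 1, 2, or 3" and its solicited-event counterpart. No temperature or fever variable appears. A predictor that a child lacks is left out of that child's model.

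The outcome is scored later. SAP 3.3 has "Respiratory Rate and Cough: determined at Outcome Assessment Visit #1", and takes fever from the 24 hours before that visit or from the visit itself. The visit window is Day 6 to Day 10 (SAP 4.1). Under SAP 6.5.5 a child with adequate clinical response but unresolved symptoms gets OCR 5, worse than any solicited-event grade.

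The later daily data are collected. Protocol 9.2.1 says "the presence and severity of cough (Table 2) will be recorded daily for the duration of the study", Protocol 8.1 says "All subjects will complete a subject memory aid from the time of enrollment through Visit 3", and Protocol 7.2 includes daily temperature in the diary. SAP 8.2.7 plans diary cough "tabulated by day from Day 1 to Day 25 (as recorded from the memory aid", and SAP 6.5.2 refers to parent-reported temperatures on the solicited events form.

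**The concern.** The primary analysis imputes missing DOOR values assuming data are missing at random given the listed predictors. If attendance at OAV#1 depends on how the child is around Days 6-10, Day 1-5 items carry that information only at a distance. A child who was coughing and did not attend is then imputed with too good a rank. If this happens more in one arm, the estimated probability of a better DOOR shifts toward that arm.

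Three groups can have Day 6-10 diary entries that the model ignores:

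- children who missed OAV#1 but were seen at OAV#2, a pattern that the worst-case rule in SAP 8.2.2.5 already provides for;
- children with an early termination visit after Day 5, where Appendix A of the protocol has the diary reviewed;
- children who attended OAV#1 with a component missing.

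Using later data is consistent with the plan. The observed OAV#2 OCR is already a Visit #1 predictor, and the Visit #2 list uses the same daily items to Day 18, so Days 6-10 already exist as analysis variables.

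**Working it through.** **1. The plan's own figures.** SAP 5 states "A sample size of 360 (180 per arm) provides 90% power using a 2-sided alpha=0.05 with a Wilcoxon Mann-Whitney U test" at p = 0.60. Noether's formula gives N = (1.960 + 1.282)² / (12 × 0.5 × 0.5 × 0.10²) = 10.507 / 0.03 = 350.2, so 351. The stated 360 is within 3%, and 360 / 0.90 = 400. The plan therefore allows for 40 of 400 children (10%) without an evaluable outcome. The sample size is not in dispute.

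**2. Scale.** With 200 per arm and no tie correction, the null standard error of the DOOR probability is √[401 / (12 × 200 × 200)] = √0.000835 = 0.029. The design effect is 0.60 − 0.50 = 0.10.

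**3. What Day 6-10 cough adds.** The documents give no correlation between days, so this step is a simulation over assumed values: day-to-day correlation 0.5, 0.7 or 0.9; child-level share of variance 0.2 or 0.5; grade 2-3 cough cut-off at 5% or 10%; 12 scenarios in all.

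- For OCR 5, R² is 0.03-0.25 with Day 1-5 items, 0.06-0.28 with OAV#2 OCR added, and 0.17-0.35 with OAV#2 OCR and Day 6-10 cough. Beyond the planned items, the gain runs from 0.299 − 0.234 = 0.065 to 0.250 − 0.097 = 0.153.
- For the whole OCR, R² is 0.27-0.49 with the planned items and 0.36-0.52 with Day 6-10 cough added. The gain runs from 0.519 − 0.485 = 0.034 to 0.386 − 0.281 = 0.105.

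**4. Effect on the primary estimate, first simulation.** Settings: 200 per arm, 10-11% missing, daily cough correlation 0.85-0.93, OAV#2 OCR kept throughout, and grade 2-3 cough at the visit multiplying the odds of missingness by 4.5.

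- Bias is +0.005 to +0.010 as planned and +0.003 to +0.004 with Day 6-10 cough. If the ends of the ranges pair up, the cut is 0.002/0.005 = 40% to 0.006/0.010 = 60%.
- In the opposite direction, bias is −0.003 to −0.008 as planned and −0.0015 to −0.0035 with the added items.

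**5. Effect on the primary estimate, second simulation.** Settings: N = 400, correlation 0.7, child-level share 0.4, cut-off 10%, 20 imputations. Short-course children with grade 2-3 cough on Days 6-10 miss OAV#1 at 4 times the nominal rate, all others at 0.7 times. Positive bias favours short course.

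| Missing overall | Day 1-5 items only | With OAV#2 OCR (as planned) | Day 6-10 cough instead of OAV#2 OCR | Cut against plan |
|---|---|---|---|---|
| 5% | +0.0056 | +0.0055 | +0.0028 | 0.0027/0.0055 = 49% |
| 11% | +0.0101 | +0.0091 | +0.0052 | 0.0039/0.0091 = 43% |
| 16% | +0.0194 | +0.0187 | +0.0116 | 0.0071/0.0187 = 38% |

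With data missing completely at random (5-15%), bias is at most 0.002 in every model and the standard error is 0.029-0.030 in all of them.

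**6. Precision.** The first simulation shows between-imputation variance falling by 20-40%. In the second, that component is 0.054 of total variance under the planned items at 10% missing completely at random. A 40% cut would change the standard error by a factor of √(1 − 0.40 × 0.054) = 0.989, about 1%. The case rests on bias, not precision.

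**7. Limits.** Both simulations give every missing child Day 6-10 entries, so the gains are upper limits. The second drops OAV#2 OCR when it adds Day 6-10 cough, and omits the site, antibiotic, age and setting indicators. It uses five daily cough items rather than a summary and does not test temperature. Neither reports the effect of donor loss.

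**The case against.** The strongest reply is that the gap is narrow and its benefit unproven.

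- **The list does not end at Day 5 as a whole.** A reader might infer that nothing later is used. Observed OAV#2 OCR is listed, so only the daily items stop there. Adequate response, solicited events and antibiotic days in the Visit #1 DOOR are themselves Day 1-5 quantities, so only the symptom component is affected. This stands.
- **The unused data are not shown to be the best predictors.** In the simulation, Day 6-10 cough beat OAV#2 OCR for the symptom component in all 12 scenarios. For the whole OCR, OAV#2 OCR added as much or more in all 12.
- **Relapse in the short arm is not hidden on Days 1-5.** Its active drug ends on Day -1, so Days 1-5 are its first days off antibiotic, and they are in the model.
- **Not every missing child gains.** Protocol 6.5 has diary information transcribed, with the diary itself not collected. A child lost before Day 6, or whose diary was never reviewed, has no usable entries. The documents do not give the share who would.
- **Sensitivity analyses exist.** Complete-case, according-to-protocol and worst-case analyses are prespecified, and the worst case is far harsher than the bias modelled here. They show how fragile the result is, but do not improve the primary estimate.

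Protocol 11.4.1 also names DOOR components from an early termination visit as imputation inputs, and SAP 8.4.1 lists none. That is a related but separate gap.

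**Conclusion.** The omission is plain on the documents: the symptom component is scored on Days 6-10, the diary covers those days, and the Visit #1 imputation uses neither its cough nor its temperature. The consequence is modest. At about 10% missing, with visit-time cough driving attendance, bias is about 0.005-0.010. That is 0.005/0.029 = 0.17 to 0.010/0.029 = 0.34 of a standard error, and up to a tenth of the design effect. Adding Day 6-10 cough removes roughly a third to a half. If data are missing completely at random, there is almost nothing to gain.

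These figures rest on assumed correlations, an assumed strong missingness mechanism and full diary availability. They do not support saying that the added items would largely restore missingness at random, because a clear residual bias remains in both simulations. Nor do they support extending the Visit #2 list to Days 19-25. The diary ends at OAV#2, so a child who misses it has no later scheduled visit at which those days would be transcribed. The point is a cheap improvement to the primary imputation, not a flaw that threatens the conclusion.

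**What to change.** Before unblinding, append two items to the Visit #1 list in SAP 8.4.1, after the Day 5 items:

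1. worst diary cough grade (0-3) over the recorded days in Days 6-10;
2. any diary temperature of at least 38.3 C over the recorded days in Days 6-10 (yes/no).

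State that an item counts as observed when at least one of those days is recorded, and fix its place in the order, since the SAP ties exact replication to ordering and seeds. Keep OAV#2 OCR and the rule that omits predictors a child lacks. Leave the Visit #2 list unchanged.

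The cost is SAP wording and two predictors, with no new data. The downside is that complete-case children without these items drop out as donors from the affected subject-specific models. Two summaries rather than ten separate daily items (five days × two measures) keep that loss small. Reporting how many imputed children had the items, and how many donors each model kept, would show what the change achieved.

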- Separately for Outcome Assessment Visit #1 and #2, using CC cohorts, a forest plot of 95% confidence intervals for the risk difference of adequate clinical response as well as the following interventions for persistent or worsening pneumonia: (1) ED/clinic visits, (2) hospitalizations, (3) surgical procedures, and (4) non-study systemic antibiotics. Tests for differences in proportions between treatment arms will be given by Fisher's exact tests.
 - Separately for Outcome Assessment Visit #1 and #2, using CC cohorts, a forest plot of 95% confidence intervals for the risk difference of adequate clinical response as well as the following interventions for all causes: (1) ED/clinic visits, (2) hospitalizations, (3) surgical procedures, and (4) non-study systemic antibiotics. Tests for differences in proportions between treatment arms will be given by Fisher's exact tests.
 - Analysis of the ordinal clinical response at Outcome Assessment Visits #1 and #2. The ITT analysis will treat the ordinal clinical response as Normal distributed and use multiple imputation to compute confidence intervals for the mean ordinal clinical response by treatment assignment and to test whether the mean ordinal clinical response varies by treatment assignment. CC, ATP, and worst case analyses of the ordinal clinical response will be performed; separately for Outcome Assessment Visit #1 and #2, a cumulative difference plot with respective 95% confidence bands for the ordinal clinical response (and an associated result from a Mantel-Hantzel chi-square test on the ordinal clinical response) will be computed. Non-inferiority analyses of the ordinal clinical response at Outcome Assessment Visits #1 and #2 using the ITT cohort, to be specified in the statistical analysis plan, may be carried out.

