3.3. Study Definitions and Derived Variables

DOOR is defined as follows:

1. Each subject is evaluated according to the ordinal composite outcome (See [Table 1](#)) and assigned an outcome rank ranging from 1-8. The ordinal outcome is referred to elsewhere in the SAP as the ordinal clinical response (OCR).
2. Desirability of Outcome Ranking (DOOR) is then assigned according to two rules:
 - i. When comparing two subjects with different ordinal responses, the subject with a better ordinal response receives a higher rank.
 - ii. When comparing two subjects with identical ordinal responses, the subject with fewer days of antibiotic use receives a higher rank.

The ordinal composite outcome involves an assessment of whether the subject has an adequate clinical response and whether they have experienced any solicited events as defined in [Table 1](#).

Table 1: Ordinal Outcome

	Adequate clinical response¹ (Assessed at Outcome Assessment Visits #1 and #2)	Solicited events³ (Assessed at Outcome Assessment Visits #1 and #2)
1	Yes, with resolution of symptoms ²	None
2	Yes, with resolution of symptoms ²	Mild (Grade 1)
3	Yes, with resolution of symptoms ²	Moderate (Grade 2)
4	Yes, with resolution of symptoms ²	Severe (Grade 3)
5	Yes, with persistent symptoms of fever, tachypnea, or cough	None or any grade
6	No, with ED/clinic visit but no hospitalization	None or any grade
7	No, with hospitalization	None or any grade
8	Death from any cause	

¹ Adequate clinical response is defined as the absence of a medically attended visit to an ED or outpatient clinic or hospitalization for persistent or worsening pneumonia that occurs after randomization and receipt of at least one dose of study drug.

- Persistent or worsening pneumonia is defined as receipt of a non-study systemic antibiotic for pneumonia or treatment for a complication of pneumonia, including drainage of pleural fluid, placement of a chest tube, video assisted thoracoscopic surgery, or thoracotomy procedures.

- Note: Receipt of a non-study antibiotic will not be regarded as satisfying this definition if it is related to a new diagnosis that is unrelated to the prior diagnosis of pneumonia.

² Resolution of symptoms is defined as the absence of all of the following:

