8.2.6. Ordinal Clinical Response at Outcomes Assessment Visits #1 and #2

Analysis of the ordinal clinical response (OCR) at Outcome Assessment Visits #1 and #2. Separately for OCR at each of the two visits, a first ITT analysis (superiority/inferiority) will test the null hypothesis that

$$\Pr(\text{OCR is better in short course}) + 0.5 \Pr(\text{OCR is equal}) = 0.5.$$

A second ITT analysis (non-inferiority) will test the null hypothesis that

$$\Pr(\text{OCR is better in short course}) + 0.5 \Pr(\text{OCR is equal}) < 0.4.$$

ITT, CC, ATP, and worst case analyses will plot cumulative difference plots and test whether the overall distributions of OCR are equivalent between the treatment arms for OCR at each of the two visits.

Cumulative difference plots (Figure 15, Figure 16, Figure 17, Figure 18 and Figure 19, Figure 20, Figure 21, Figure 22) are produced as follows. For $i \in \{1,2,3,4,5,6,7\}$, the difference in proportions of subjects with $\text{OCR} \leq i$ between treatment arms is plotted (i on x-axis and

difference in proportion on y-axis), together with 95% confidence intervals computed using the Newcombe method with continuity correction.

For CC-V1, CC-V2, ATP-V1, and ATP-V2 analysis populations, OCRs will be summarized by treatment group and tests of overall distributions of OCR will be performed using the mean score statistic (QS). The mean score statistic is obtained from PROC FREQ in SAS using the “chisq” option and is denoted in output as the “Mantel-Haenszel Chi-Square” statistic.

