8.2.6.1. ITT Analyses of OCR at Outcomes Assessment Visit #1

Twenty (20) multiple imputation datasets for OCR at Outcome Assessment Visit #1 will be generated in manner analogous to that described in Section 8.1.1, except using OCR at Outcome Assessment Visit #1 in place of DOOR at Outcome Assessment Visit #1 for the response. Also, analogous to Section 8.1.1, the Mann-Whitney U statistic will be computed for each of the datasets and combined using Rubin’s Rules to generate the test statistic W and a p-value for the test of the null hypothesis that

$$\Pr(\text{OCR at Outcome Assessment Visit \#1 is better in short course}) + 0.5 \Pr(\text{OCR at Outcome Assessment Visit \#1 is equal}) = 0.5.$$

The F-test using the W statistic will be inverted to produce a 95% confidence interval for $\Pr(\text{OCR is better in short course}) + 0.5 \Pr(\text{OCR is equal})$. Whether the lower bound of this confidence interval is greater than 0.4 will serve as a test of the non-inferiority null hypothesis that

$$\Pr(\text{OCR at Outcome Assessment Visit \#1 is better in short course}) + 0.5 \Pr(\text{OCR at Outcome Assessment Visit \#1 is equal}) < 0.40.$$

Results will be reported in [Table 30](#).

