Subjects requiring imputation are sorted in ascending order
by PATID.

DEFINE N=number of subjects requiring imputation

DEFINE g&i=analysis dataset containing predictors and DOOR for
CC-V1 subjects as well as subject i (only one subject not in
CC-V1 included). Note that CC-V1 subjects that are missing a
value
for one or more variables in the subject-specific imputation
model are excluded.

DEFINE imp_g&i = g&i, with 20 imputed values for the missing DOOR
added by PROC MI

DEFINE &&modelVars_&i = list of observed variables in subject i, to
be used for imputation of DOOR and OCR.

%do i=1 %to &N;

```
PROC MI data=g&i out=imp_g&i seed=1200&i NIMPUTE=20 noprint;
  var &&modelVars_&i DOOR OCR;
  monotone reg(DOOR_V1 = &&modelVars_&i);
  monotone reg(OCR_V1 = &&modelVars_&i);
```

```
run;
```

```
%end;
```

```
imp_g&i will be subset to contain only rows for the subjects with  
imputed DOOR and merged together and with CC-V1 data to create the  
twenty complete multiply imputed datasets
```

```
*****
```

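### Missing OCR is imputed as an unbounded continuous value but analysed by ties and by integer cut-points, so the ITT OCR plots are distorted when missingness differs by arm

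*SAP*

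**What the plan says.** SAP 3.3 grades each child on the ordinal outcome, "assigned an outcome rank ranging from 1-8", where 1 is best. Under SAP 6.5.1 and 6.5.5, OCR is missing for randomized children with no recorded dose of study product and, unless the child died, for children without the outcome visit.

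SAP 8.4.1 fills the gaps in PROC MI with "monotone reg(OCR_V1 = &&modelVars_&i" and "NIMPUTE=20 noprint". Neither the text nor the pseudo-code gives a minimum, a maximum, rounding, or any step that returns the draw to a rank.

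Three ITT outputs use these values:
- **Rank comparison.** For Visit #1 the datasets are "generated in manner analogous to that described in Section 8.1.1, except using OCR at Outcome Assessment Visit #1 in place of DOOR", and "the Mann-Whitney U statistic will be computed for each of the datasets and combined using" Rubin's rules. SAP 8.2.6.2 does the same for Visit #2. The estimand is Pr(better) + 0.5 Pr(equal).
- **Non-inferiority.** "Whether the lower bound of this confidence interval is greater than 0.4 will serve as a test of the non-inferiority null hypothesis" (Tables 30 and 31).
- **Plots.** "ITT, CC, ATP, and worst case analyses will plot cumulative difference plots". Each shows the arm difference in the proportion with OCR ≤ i for i = 1 to 7; the ITT versions are Figures 15 and 19.

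Protocol 11.4.2 had a different ITT analysis in view: "The ITT analysis will treat the ordinal clinical response as Normal distributed and use multiple imputation", with a comparison of means.

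**The concern.** Normal imputation suits a comparison of means, which is what the protocol described. The SAP kept that imputation but moved to analyses that depend on integer categories. A draw of 1.2 is not a possible outcome: it ranks behind every observed child at rank 1 and is counted as not OCR 1. A draw of 0.3 is not possible either: it ranks ahead of all of them. No draw can equal an observed rank, so the half-credit term for ties never applies between an imputed and an observed child.

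OCR is DOOR without the antibiotic-days tie-breaker, so it shows whether the shorter course costs anything clinically. The footnotes to SAP Tables 14 and 15 say that DOOR conclusions must rest on a detailed look at the components. An arm difference in the ITT OCR plots that comes only from the imputation model would mislead that reading.

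**Working it through.** **The plan's own figure.** The documents give no expected OCR distribution, so there is no OCR figure to reproduce. The sample-size statement supplies the arm size and the missingness. Noether's formula at p = 0.60 gives (1.960 + 1.282)² / (12 × 0.25 × 0.10²) = 350.2, against 360 stated; 360 / 0.9 = 400, or 200 per arm. The plan therefore expects about 10% loss, with no split by arm.

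**Assumptions.** Share of children at rank 1: 25% to 80%. Missingness, higher versus lower arm: 12/8, 15/5 and 20/5%, plus 10/10. No true arm difference.

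**Step 1: draws below 1.** With mean μ and SD s of OCR, the share of draws below 1 is Φ((1 − μ)/s). Because draws are continuous, this is also the share counted as OCR ≤ 1. The share that should count is the rank-1 share, and the gap between the two drives the plot error.

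**Step 2: plot error at OCR ≤ 1** = (difference in missingness) × gap.

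| Assumed share at rank 1 | Draws below 1 | Gap (points) | Error, 12/8 (0.04 × gap) | Error, 15/5 (0.10 × gap) |
|---|---|---|---|---|
| 80% | 34% | 46 | 1.8 | 4.6 |
| 65% | 28% | 37 | 1.5 | 3.7 |
| 50% | 23% | 27 | 1.1 | 2.7 |
| 50%, with 25% at rank 5 | 21% | 29 | 1.2 | 2.9 |
| 40% | 20% | 20 | 0.8 | 2.0 |
| 25% | 14% | 11 | 0.4 | 1.1 |

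At 20/5 the factor is 0.15, giving 1.7 (0.15 × 11) to 6.9 (0.15 × 46) points. The error always counts against the arm with more missing data.

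**Step 3: the OCR probability.** Let q be the probability that an imputed child ranks better than an observed one: the sum over k of π_k Φ((k − μ)/s), where π_k is the share at rank k. It should be 0.50 with ties counted as half; under these assumptions it is 0.44 to 0.47. The tie probability is 0, against 0.26 to 0.65 for two observed children. The shift in the estimate is (q − 0.5) × (difference in missingness):
- 15/5: −0.06 × 0.10 = −0.006 to −0.03 × 0.10 = −0.003, so 0.494 to 0.497.
- 12/8: −0.0024 to −0.0012.
- 10/10: zero.

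**Step 4: simulation.** 200 per arm, no true difference, 15% (short) versus 5% (standard) missing, 20 imputations from a regression on arm and a 0–3 severity covariate, and the pooled F-test of SAP 8.1.1. The tie correction was used in its standard form, with the N(N − 1) divisor that the formula printed in 8.1.1 does not show. 500 runs per row; PMM is predictive mean matching.

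| Share at rank 1 | Imputation | Estimate | Error at OCR ≤ 1 (points) | CI half-width | Non-inferiority declared |
|---|---|---|---|---|---|
| 80% | normal | 0.496 | −4.22 | 0.051 | 98.0% |
| 80% | PMM | 0.500 | +0.06 | 0.041 | 99.8% |
| 65% | normal | 0.497 | −3.25 | 0.055 | 96.0% |
| 65% | PMM | 0.500 | −0.10 | 0.050 | 97.6% |
| 40% | normal | 0.496 | −2.03 | 0.058 | 90.0% |
| 40% | PMM | 0.501 | +0.22 | 0.056 | 94.6% |

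Across the simulated settings, the rejection rate under no difference stayed at 2–6% with normal imputation. Rounding the normal draws and clipping them to 1–8 left the estimate at 0.488 to 0.495 and the error at OCR ≤ 1 at −0.7 to −2.7 points.

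**The case against.** The case for leaving the plan alone has five parts.

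- **Missingness may be balanced.** The trial is double-blind with matching placebo, the documents plan for about 10% loss overall, and nothing predicts a three-to-one imbalance. This stands: with equal missingness and no true difference there is no between-arm bias, and 15/5 is a stress case.
- **The non-inferiority call is barely touched.** A shift of 0.006 is about 12% of a 0.051 half-width (0.006 / 0.051), and 0.40 lies 0.10 from the null. This stands. The simulated differences in how often non-inferiority is declared come from trials with a bound near 0.40, and partly from the wider interval.
- **Other OCR analyses exist.** The complete-case, according-to-protocol and worst-case versions do not use these draws. This stands, and it limits the harm, but it does not make the ITT version right.
- **The per-arm share at OCR 1 is not displayed.** A reader might infer that the best-outcome share will be under-reported in each arm even with equal missingness. That is true of the imputed data, but no planned ITT output shows it. The ITT figures plot differences, and category counts are tabulated only for the complete-case and according-to-protocol cohorts.
- **DOOR is imputed the same way.** A reader might infer that the primary result is compromised. Protocol 11.4.1 specifies linear regression with DOOR treated as continuous, and in simulations of this kind the DOOR probability moved by 0.006 or less. The point does not support changing the primary imputation.

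**Conclusion.** The mismatch is certain from the SAP text: an integer outcome is imputed as an unbounded continuous value and then analysed by ties and integer cut-points. Its size rests on assumptions, because the documents give neither an OCR distribution nor missingness by arm.

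Under the assumptions above with 15% versus 5% missing, the ITT plots at OCR ≤ 1 are off by about 1 to 5 points (0.4 to 1.8 at 12% versus 8%). The OCR probability is off by 0.003 to 0.006. The plots are the material part. These are secondary analyses, so the change is advisable rather than essential.

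Two stronger readings are not supported. A reader might infer that draws below 1 flatter the arm with more missing data. They do not in the plots: such draws still count as OCR ≤ 1, and the error comes from draws above 1 that should be exactly 1. A reader might also infer a bias against the short course. The direction follows whichever arm loses more data, which the documents do not say.

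**What to change.** In SAP 8.4.1, impute OCR_V1 and OCR_V2 by predictive mean matching (`regpmm` in place of `reg` in the OCR statement) or by a cumulative-logit model, so that every imputed OCR is an observed integer category. State the number of donors, and add how Figures 15 and 19 combine the 20 datasets, which the SAP does not say. Do not round and clip the normal draws. Leave the protocol-specified DOOR imputation unchanged.

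The cost is one keyword and a short paragraph, with no new data; seeds and variable order stay as listed. The pseudo-code imputes DOOR and OCR in one call under one seed, so if the DOOR draws must not change, run OCR in its own call. SAP section 13 should also record that the ITT OCR analysis now compares ranks rather than means, since it currently reports no change from the protocol.
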